5.3.5 Packaging and Labeling

Tisotumab vedotin will be supplied in vials containing 40 mg of tisotumab vedotin as lyophilized powder. The powder must be reconstituted with 4 mL water for injection leading to a 10 mg/mL solution. Tisotumab vedotin will not be dispensed in child-resistant packaging.

Labeling will be in accordance with the EU Guidelines to Good Manufacturing Practice, Annex 13, Investigational Medicinal Products, and any other applicable local regulatory requirements.

For further details on packaging and labeling of tisotumab vedotin, please refer to the Pharmacy Binder.

5.3.6 Preparation

The dose of tisotumab vedotin for administration must be prepared by the trial site pharmacy using aseptic technique. The reconstituted tisotumab vedotin must be diluted into a 0.9% NaCl infusion bag containing 100mL according to the dose calculated for the patient.

The infusion must be completed within 24 hours after the tisotumab vedotin vials have been reconstituted. A 0.2 μ m in-line filter must be used for the infusion. The entire (100 mL or

greater) infusion volume from the prepared infusion bag needs to be administered; no dead volume is provided.

Detailed drug preparation instructions are provided in the Pharmacy Binder.

5.4 Required Ocular Premedication and Preventive Eye Therapy

In order to prevent ocular AEs, all patients must adhere to ocular premedication and preventive eye therapy guidelines listed below (see also [Appendix C](#)):

- Administration of local ocular vasoconstrictor before infusion (brimonidine tartrate 0.2% eye drops or similar, 3 drops in each eye immediately prior to start of infusion; otherwise to be used in accordance with the product prescribing information). If the patient does not tolerate ocular vasoconstrictors due to adverse reactions, continued treatment with these may be stopped at the discretion of the investigator and following discussion with the sponsor's medical monitor.
- Use of eye cooling pads during infusion, e.g., Cardinal Health cold packs, refrigerator-based THERA PEARL Eye Mask, or similar. To be applied 5 minutes prior to start of infusion in accordance with the instructions provided with the eye cooling pads. The cooling pads must remain on the patient's eyes during the entire 30-60 minute infusion and for as long as 30 minutes afterwards.
- Application of steroid eye drops (dexamethasone 0.1% eye drops or equivalent) before and after each infusion for a total of 4 days. The first drops are to be given 24 hours prior to start of infusion. Continue treatment for 72 hours thereafter. Steroid eye drops should be administered as 1 drop in each eye, 3 times daily, or used in accordance with the product prescribing information.
- Use of lubricating eye drops during the whole treatment phase of the trial (i.e., from first dose of study drug until 30 days after the last dose of study drug). Frequent use of lubricating eye drops as per standard of care for patients receiving chemotherapy is recommended. Lubricating eyedrops should be self-administered daily or as needed according to the package insert or prescribed instructions from the ophthalmologist.
- It is recommended that patients not wear contact lenses while being treated with tisotumab vedotin from the first dose until 30 days after the last dose of study drug.

5.5 Concomitant Therapy

All concomitant medications, blood products, and radiotherapy administered will be recorded from Day 1 (predose) through the safety reporting period. Any concomitant medication given for a study protocol-related adverse event should be recorded from the time of informed consent. Exceptions to this include medications administered for ocular AEs, which must be documented until resolution of the AE, return to baseline, or study closure, whichever comes first.

5.5.1 Required Concomitant Therapy

Please see Section [5.4](#) and [Appendix C](#) for required ocular premedication and preventive eye therapy schedule.

5.5.2 Allowed Concomitant Therapy

Use of the DigniCap Scalp Cooling System or other, similar scalp-cooling device according to guidelines is permitted to prevent alopecia if available at the clinical study site.

Anti-coagulation therapy for prophylaxis/treatment of thrombotic conditions is permitted with the following restrictions:

- A patient on anticoagulants when entering the study must be on a steady dose at least 4 weeks prior to study drug administration and must have INR and aPTT monitored prior to dosing. Patients on anticoagulation therapy requiring monitoring of the PT/INR should have their doses adjusted to target an INR ≤ 2.5 ULN at least 4 weeks prior to study drug administration. Coagulation parameters including fibrinogen, aPTT, PT, and INR must be measured locally prior to each dose of study drug as specified in Section [7.7.2](#).
- If a patient develops a new DVT/PE and requires initiation of therapeutic anticoagulation, therapy with tisotumab vedotin will be held until new anticoagulation has been started, and:
 - For vitamin K antagonists, patient must have been on a steady dose for at least 2 weeks with INR < 2.5 . Parenteral low molecular weight heparin (LMWH) must no longer be required for bridging.
 - For other anticoagulant agents that require additional parenteral agents during initiation, the parenteral agent must have been discontinued, and the anticoagulant must be on a steady dose for at least 2 weeks. (for e.g., edoxaban for new DVT/PE events, which can be started after an initial 5–10 days of parenteral anticoagulant as per the product label).
 - For agents that require a higher dose during initiation, (e.g., apixaban that is started at 10 mg orally twice per day, and then maintained at 5 mg twice per day), tisotumab vedotin will be held during initiation and can be resumed after 2 weeks on the stable maintenance dose.
 - For agents such as LMWH that are administered via weight-based dosing, tisotumab vedotin will be held during the initial 2 weeks of the introduction of new anticoagulant.
- Chronic use of antiplatelet therapy (ASA [aspirin], clopidogrel, and similar medications), as required for vascular diseases such as coronary artery disease, cerebrovascular accident, and similar conditions, is permitted on this study.

- A patient cannot receive both anticoagulant(s) and antiplatelet agent(s) concurrently while on study.

Each patient should be told to notify the trial site about any new medications they are taking after receiving the first tisotumab vedotin administration. All medications (other than tisotumab vedotin) and significant non-drug therapies (including herbal/natural medications, and blood transfusions) administered during the trial must be recorded in the eCRF.

Investigators may prescribe concomitant medications or treatments deemed necessary to provide adequate supportive care except for those medications identified as prohibited (Section 5.5.3). Administration of concomitant medications must be reported in the appropriate section of the eCRF along with dates of administration and reasons for use.

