- Platelet count $\geq 100 \times 10^9/\text{L}$ assessed at least 2 weeks after transfusion with blood products.
- Hemoglobin $\geq 5.6 \text{ mmol/L}$ (9.0 g/dL) assessed at least 2 weeks after transfusion with blood products.
- Serum bilirubin $\leq 1.5 \times$ upper limit of normal (ULN) or direct bilirubin $\leq 2 \times$ ULN in patients diagnosed with Gilbert’s syndrome.

- Estimated glomerular filtration rate (eGFR) ≥ 50 mL/min/1.73m² using the Modification of Diet in Renal Disease (MDRD) study equation as applicable.
- Alanine aminotransferase (ALT) and aspartate aminotransferase (AST) $\leq 2.5 \times$ ULN. (If liver tumor/metastases are present, then $< 5 \times$ ULN is allowed).

8. Acceptable coagulation status:

- INR ≤ 1.2 without anticoagulation therapy.
- aPTT ≤ 1.25 ULN.

9. Life expectancy of at least 3 months.

10. Patients of childbearing potential as defined in Section 4.3, under the following conditions:

- Must have a negative serum or urine pregnancy test (minimum sensitivity 25 mIU/mL or equivalent units of beta human chorionic gonadotropin [β -hCG]) result within 7 days prior to the first dose of tisotumab vedotin. Patients with false positive results and documented verification that the patient is not pregnant are eligible for participation.
- Must agree not to breastfeed or donate ova, starting at time of informed consent and continuing through 6 months after the final dose of study drug administration.
- Must agree to complete abstinence or, if sexually active in a way that could lead to pregnancy, must consistently use 2 highly effective methods of birth control (as defined in [Appendix F](#)) starting at time of informed consent and continuing throughout the study and for at least 6 months after the final dose of study drug administration.

11. Able to provide fresh or archival tissue for biomarker analysis. Fresh tissue must be obtained from a newly obtained core or excisional biopsy of a tumor lesion. Archived specimens must have been collected within 2 years of first administration of tisotumab vedotin. Older specimens may be allowed upon approval of the sponsor's medical monitor.

12. The patient or the patient's legally authorized representative must provide written informed consent.

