5.3.3 Other Adverse Events

AEs such as increased bleeding, hemorrhage, elevated liver enzymes, mucositis, neutropenia, and peripheral neuropathy may be associated with tisotumab vedotin administration. Dose modification and toxicity management are provided in [Table 7](#).

Table 7: Dose modification and toxicity management for other AEs associated with tisotumab vedotin

Bleeding Events	

 Control vital signs and ensure stabilization of the patient according to local standards. Prompt evaluation to identify the underlying etiology of the bleeding event. Management should ultimately be dictated by the underlying diagnosis. Control laboratory coagulation and hematologic parameters including PT, aPTT, fibrinogen, platelets, INR and hemoglobin as soon as possible. 	
All Patients	
Any grade pulmonary or CNS hemorrhage	Permanently discontinue tisotumab vedotin treatment.
Patients NOT on anticoagulation therapy	
1st occurrence	Hold dosing until:
Hemorrhage (other) ¹ Grade 3	
 a) Bleeding has resolved. b) Blood hemoglobin level is stable. c) There is no bleeding diathesis that could increase the risk of continuing therapy. d) Patients must not have tumors involving or adjacent to major blood vessels 
When the above criteria are fulfilled the patient can resume treatment with tisotumab vedotin at the same dose as prior to the event.

≥2nd occurrence	Contact sponsor in order to discuss whether the patient may continue or must permanently discontinue tisotumab vedotin treatment.
Hemorrhage (other) ¹ Grade 3	
Hemorrhage Grade 4 (any occurrence)	Patient must permanently discontinue tisotumab vedotin treatment
Patients on anticoagulation therapy	
INR >2.5	
Patients on therapeutic anticoagulation whose INR is >2.5 prior to infusion of tisotumab vedotin must hold tisotumab vedotin until INR is ≤2.5. Patients may resume tisotumab vedotin administration immediately after the INR is ≤2.5.
 
Strongly consider holding anticoagulation until the above parameters are met.

Hemorrhage (other) ^a Grade 3	
Hold anticoagulation therapy.
 
Contact sponsor in order to discuss whether the patient may continue or must permanently discontinue tisotumab vedotin treatment.

Hemorrhage Grade 4 (any occurrence)	Patient must permanently discontinue tisotumab vedotin treatment
Liver parameters elevated (AST, ALT, or bilirubin)	

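### The anticoagulation target in Protocol 5.5.2 is a multiple of ULN, while Table 7 holds tisotumab vedotin at an absolute INR above 2.5, so a patient on target can still be held

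*Protocol*

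**What the plan says.** **Titration target.** Protocol 5.5.2, on patients already taking anticoagulants at entry, says that those needing PT/INR monitoring "should have their doses adjusted to target an INR" at or below "2.5 ULN at least 4 weeks prior to study drug administration". The same bullet adds that "INR must be measured locally prior to each dose of study drug".

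**Hold rule.** Protocol 5.3.3, Table 7, states: "Patients on therapeutic anticoagulation whose INR is >2.5 prior to infusion of tisotumab vedotin must hold tisotumab vedotin". On restarting: "Patients may resume tisotumab vedotin administration immediately after the INR is ≤2.5". On the anticoagulant itself: "Strongly consider holding anticoagulation until the above parameters are met". The Table 7 rule does not mention ULN.

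**Other INR limits.** For a vitamin K antagonist started for a new DVT or PE, 5.5.2 asks for a steady dose for "at least 2 weeks with INR < 2.5". Inclusion criterion 8 in 4.1 sets an INR of at most 1.2 in patients without anticoagulation. Both are absolute.

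**Meaning of ULN.** Inclusion criterion 7 defines the term ("upper limit of normal (ULN) or direct bilirubin"), and criterion 8 uses it as a multiplier for aPTT (at most 1.25 ULN). The documents give no numerical ULN for INR.

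**The concern.** The titration target and the hold threshold apply to the same patients and the same laboratory value, so the target should not lie above the level that stops treatment. As written, it does at any site whose laboratory ULN is above 1.0. Of the four INR limits in the protocol, only the 5.5.2 target is tied to ULN, which suggests a drafting slip.

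At stake is the conduct of treatment. A patient titrated in line with 5.5.2 could arrive for an infusion and have it held, possibly from the first one, because 5.5.2 also asks for a steady anticoagulant dose for at least 4 weeks beforehand. The site would then be told to think seriously about pausing the anticoagulant. That matters in a disease where Protocol 1.2.1 cites venous thromboembolism in as many as 42% of patients.

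**Working it through.** The plan states no figure to reproduce. The check compares two thresholds.

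**Inputs**
- 5.5.2 target: INR at most 2.5 × ULN, reading ULN as a multiplier, as in inclusion criterion 8.
- Table 7 limit: hold above 2.5, resume at 2.5 or below.
- Measurement: local, before each dose (5.5.2; also 7.7.2).
- ULN for INR: not in the documents. Assumed 1.0 to 1.2. The upper value is borrowed from the inclusion limit without anticoagulation, purely as a reference point; it is not a laboratory ULN.

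**Formula**

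Gap = 2.5 × ULN − 2.5 = 2.5 × (ULN − 1)

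That is 0.25 INR units for each 0.1 of ULN above 1.0.

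| Assumed ULN | 5.5.2 target, up to | Table 7 limit | Gap |
|---|---|---|---|
| 1.0 | 2.5 × 1.0 = 2.50 | 2.5 | 0 |
| 1.1 | 2.5 × 1.1 = 2.75 | 2.5 | 0.25 |
| 1.2 | 2.5 × 1.2 = 3.00 | 2.5 | 0.50 |

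**Example.** Take an INR of 2.7 at a site with an assumed ULN of 1.1. Since 2.7 ≤ 2.75, the patient is on target under 5.5.2. Since 2.7 > 2.5, Table 7 requires a hold.

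**Condition.** The 5.5.2 target exceeds the Table 7 limit exactly when ULN is above 1.0. This follows from the two rules and needs no assumed value; only the size of the gap does. Because testing is local, the target can differ between sites while the hold limit cannot.

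**After the change.** With ULN removed, the target is 2.5 at every site and the gap is 2.5 − 2.5 = 0.

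**The case against.** The strongest reply is that the two rules do not contradict each other. 5.5.2 is advisory: it gives a target to aim for, set at least 4 weeks before study drug. Table 7 is mandatory and is applied before each infusion. A patient at INR 2.7 can be within the target and also be held, with both rules obeyed. This stands. The thresholds are misaligned rather than incompatible, and 5.5.2 sets a target, not a ceiling. The same misalignment runs the other way if a local ULN is below 1.0: the target then falls below 2.5, and a patient above target may still be dosed.

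A reader might infer that 5.5.2 lets patients be dosed at an INR as high as 3.00. The documents do not support that. Table 7 stops treatment above 2.5, INR is measured before each dose, and 7.7.2 requires coagulation results to be reviewed within 24 hours before treatment.

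It can also be said that holds will occur whatever the target, since a patient aimed at 2.5 or below can exceed it on the day. This stands too. The change can remove only holds that arise from titrating above 2.5 on a literal reading of ULN, and nothing shows how many patients that would be. Anticoagulants without INR monitoring are also permitted. The holds are therefore possibly avoidable, no more.

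What the reply does not explain is why a titration target should lie above the treatment-stopping limit at all.

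**Conclusion.** The point holds as a misalignment of thresholds in operative treatment instructions. Wherever the local ULN for INR exceeds 1.0, a patient titrated on target under 5.5.2 can be held under Table 7 and considered for anticoagulation interruption. The gap is 0.25 INR units at an assumed ULN of 1.1 and 0.50 at 1.2; it is zero at 1.0. It rests on reading ULN in 5.5.2 as a multiplier, which is how 4.1 uses it, and on ULN values that the documents do not supply. The share of patients on INR-monitored anticoagulants is not given either, so the number affected cannot be computed.

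The practical effect is limited. Treatment may resume as soon as INR is back to 2.5 or below. In the dose-dense schedule, 5.2.3 drops a Day 8 dose held for more than 2 days because of toxicity, but the protocol does not say whether an INR hold counts as one, so lost doses should not be assumed. A reader might also infer an effect on the trial's results. No endpoint definition, analysis set or decision rule depends on either threshold, so the documents do not support that. This is a minor correction worth making.

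**What to change.** Delete ULN from the 5.5.2 target so that it reads INR ≤ 2.5, matching Table 7 at every site. Leave the restart condition for a new vitamin K antagonist (INR below 2.5) as it is: it serves a separate purpose and differs from Table 7 only at exactly 2.5.

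The edit is one word in one protocol section, with no change to the SAP, sample size or schedule of assessments. Because protocol amendments go to the IRB/IEC (10.2), it is best carried in the next amendment and does not justify one of its own.

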5.5.3 Prohibited Concomitant Therapy

Patients must be instructed not to take any medications, including over-the-counter products, without first consulting with the investigator.

The following is prohibited:

- Curative intent radiation therapy, from the time of consent until the patient completes the trial, with the following exceptions:
 - Radiation therapy of a solitary non-target lesion IS allowed.
 - Palliative radiotherapy IS allowed as per RECIST criteria.
- Drugs and substances known to be strong CYP3A and/or P-gp inhibitors according to the US FDA's list of drug interactions should be avoided if possible. If administered, the patient must be closely observed for potential adverse reactions.

Patients may not receive other investigational drugs, immunosuppressive medications, or systemic anti-neoplastic therapy during the study.

5.6 Management of Adverse Reactions

5.6.1 Management of Infusion Reactions

IRRs may occur during the infusion of study treatment. The infusion should be administered at a site properly equipped and staffed to manage anaphylaxis should it occur. If anaphylaxis occurs, administration of tisotumab vedotin should be immediately and permanently discontinued.

All supportive measures consistent with optimal patient care should be given throughout the study according to institutional standards. Supportive measures may include extending the infusion time and/or administering medications for IRRs.

All patients should be observed for 2 hours after ending their first infusion of study drug and 15 minutes for all subsequent cycles. In case any clinically significant IRR is observed during or after the first infusion of study drug or at subsequent treatment cycles, the patient

should be observed for 2 hours after end of study drug administration for all following infusions.

For more information on infusion reactions, please refer to Section 5.3.2.

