5.3.2 Infusion-Related Reactions

Tisotumab vedotin may cause IRRs including severe hypersensitivity or anaphylaxis. Signs and symptoms usually develop during or shortly after drug infusion.

- In case any clinical significant IRR is observed during or after the first infusion of tisotumab vedotin or at subsequent treatment cycles, the patient should be observed for 2 hours after the end of tisotumab vedotin administration for all subsequent infusions.
- At all times during infusion, immediate emergency treatment of an anaphylactic reaction according to institutional standards must be assured. In order to treat possible anaphylactic reactions, for instance, dexamethasone 10 mg and epinephrine in a 1:1000 dilution or equivalents must always be available along with equipment for assisted ventilation.
- All premedication must be reported on the concomitant medication page in the eCRF.

Dose modification and toxicity management guidelines for tisotumab vedotin associated infusion reaction are provided in [Table 6](#).

Table 6: Dose modification and toxicity management for infusion-related reactions

Infusion-Related Reactions (IRRs)	
Grade 1	Continue infusion at the investigator's discretion at half the infusion rate under close medical supervision.
Grade 2	Infusion must be interrupted and appropriate medical management instituted. The infusion may be re-started at the investigator's discretion at half the infusion rate under close medical supervision, if symptoms have resolved to \leq Grade 1 within an hour. The patient should be pre-medicated (antihistamine, acetaminophen and corticosteroids are recommended) before the next infusion.
Grade 3 1st occurrence	Infusion must be interrupted and appropriate medical management instituted. The infusion may be re-started at the investigator's discretion at half the infusion rate under close medical supervision if symptoms have resolved to \leq Grade 1 within an hour. The patient should be pre-medicated (antihistamine, acetaminophen and corticosteroids are recommended) before the next infusion.
Grade 3 2nd occurrence despite premedication	Permanently discontinue tisotumab vedotin treatment.
\geq Grade 4	Infusion must be interrupted immediately and appropriate medical therapy must be administered. Permanently discontinue tisotumab vedotin treatment.

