7.7.8.2 Procedures for Eliciting and Recording Adverse Events

Eliciting Adverse Events

An open-ended or non-directed method of questioning should be used at each study visit to elicit the reporting of AEs.

Recording Adverse Events

The following information should be recorded on the Adverse Events and Pre-existing Conditions CRF:

- Description including onset and resolution dates
- Whether it met SAE criteria
- Severity
- Relationship to study treatment or other causality
- Outcome

Diagnosis vs. Signs or Symptoms

In general, the use of a unifying diagnosis is preferred to the listing out of individual symptoms. Grouping of symptoms into a diagnosis should only be done if each component sign and/or symptom is a medically confirmed component of a diagnosis as evidenced by standard medical textbooks. If any aspect of a sign or symptom does not fit into a classic pattern of the diagnosis, report the individual symptom as a separate adverse event.

Important exceptions for this study are adverse reactions associated with the infusion of study drug. For IRRs, do not use the NCI CTCAE terms of “cytokine release syndrome,”

“acute infusion reaction,” or “allergic or hypersensitivity reaction.” Instead, record each sign or symptom as an individual AE. If multiple signs or symptoms occur with a given infusion-related event, each sign or symptom should be recorded separately with its level of severity.

Recording Serious Adverse Events

For SAEs, record the event(s) on both the CRF and an SAE form.

The following should be considered when recording SAEs:

- Death is an outcome of an event. The event that resulted in the death should be recorded and reported on both an SAE form and CRF.
- For hospitalizations, surgical, or diagnostic procedures, the illness leading to the surgical or diagnostic procedure should be recorded as the SAE, not the procedure itself. The procedure should be captured in the narrative as part of the action taken in response to the illness.

Progression of the Underlying Malignancy

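### The infusion-reaction rules give no stated observation period for the dose-dense Cycle 1 Day 8 and Day 15 infusions, and Table 6 is not tied to the anaphylaxis rule in Protocol 5.6.1

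*Protocol*

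**What the plan says.** **Observation after infusion.** Protocol 5.6.1 has every patient watched for 2 hours after the "first infusion of study drug and 15 minutes for all subsequent cycles". A further sentence, in both 5.3.2 and 5.6.1, requires 2 hours after every later infusion once a clinically significant reaction has been seen. Its trigger is a reaction during or after the first infusion, or at subsequent treatment cycles.

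**Dose-dense schedule.** Protocol 5.1 gives infusions on Days 1, 8 and 15 of each 4-week cycle. The visit lists for Day 8 (6.4.4) and Day 15 (6.4.5) contain no observation period. Section 3.1.1 sets the DLT window at 28 days from the first dose.

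**Anaphylaxis.** Protocol 5.3.2 opens: "Tisotumab vedotin may cause IRRs including severe hypersensitivity or anaphylaxis". It then says: "Dose modification and toxicity management guidelines for tisotumab vedotin associated infusion reaction are provided in" Table 6. That table sorts reactions by grade:
- After a first Grade 3 reaction the infusion is interrupted. It may be restarted at half rate, at the investigator's discretion, if symptoms have come down to Grade 1 or lower within an hour. Premedication is then given before the next infusion.
- A second Grade 3 reaction despite premedication ends treatment.
- At Grade 4 or higher: "Infusion must be interrupted immediately and appropriate medical therapy must be administered. Permanently discontinue tisotumab vedotin treatment".

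Protocol 5.6.1 has a rule that does not depend on grade: "If anaphylaxis occurs, administration of tisotumab vedotin should be immediately and permanently discontinued". It closes by sending the reader to 5.3.2. Neither 5.3.2 nor Table 6 points back.

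**The concern.** The observation rule divides infusions into the first one and those in later cycles. That covers every infusion when there is one per cycle, but not when there are three. The second and third exposures to the dose-dense regimen, the regimen that the run-in exists to test for safety, then have less stated monitoring than infusions in Cycle 2 and beyond.

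The anaphylaxis rule sits outside the table that sites are told to use. A site working from Table 6 alone finds no anaphylaxis row and no pointer to 5.6.1. It could take the optional restart as open to an anaphylactic reaction that it had graded 3, although another section takes that patient off drug permanently. Both matters concern patient safety and uniform conduct across sites. Neither bears on the sample size, the response-rate intervals or the interim futility rule.

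**Working it through.** No formula applies and the plan states no figure to reproduce. The check is to set the passages side by side.

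**1. Which infusions does the observation sentence cover?**

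| Infusion | First infusion? | In a subsequent cycle? | Stated period, no prior reaction |
|---|---|---|---|
| Q3W, Cycle 1 Day 1 | yes | no | 2 hours |
| Q3W, Cycle 2 onward | no | yes | 15 minutes |
| Dose-dense, Cycle 1 Day 1 | yes | no | 2 hours |
| Dose-dense, Cycle 1 Day 8 | no | no | none stated |
| Dose-dense, Cycle 1 Day 15 | no | no | none stated |
| Dose-dense, Cycle 2 onward | no | yes | 15 minutes |

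On the dose-dense schedule 3 − 1 = 2 of the three Cycle 1 infusions fall under neither limb. Days 8 and 15 both lie within 28 days of the first dose, so for run-in patients both are in the DLT window.

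Planned dose-dense patients number about 12 (run-in) + 30 (one Part A arm) + 80 (Part B) = 122. If the dose-dense arm of Part A were the one expanded, the total would be up to 122 + 70 = 192. These are planned enrolments under Protocol 9.1 and the Synopsis, taking the run-in at its upper figure of 12.

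**2. Does anything else fill the gap?** The trigger sentence in 5.3.2 and 5.6.1 uses the same first-infusion and later-cycle wording. Read the same way, a reaction first seen on Cycle 1 Day 8 does not clearly set off the 2-hour rule for the infusions that follow. The Day 8 list (6.4.4) has only predose blood samples. The Day 15 list (6.4.5) has Cycle 1 PK samples at 1 and 5 hours after infusion, which may keep a patient on site but are not an observation rule. Section 5.4 keeps cooling pads on for as long as 30 minutes after infusion, for ocular protection.

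**3. Where do Table 6 and 5.6.1 agree and where can they part?**

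| Anaphylactic reaction handled as | Table 6 | 5.6.1 |
|---|---|---|
| Grade 4 or higher | permanent discontinuation | permanent discontinuation |
| Grade 3, second, despite premedication | permanent discontinuation | permanent discontinuation |
| Grade 3, first | restart permitted if resolved to Grade 1 or lower within an hour | permanent discontinuation |

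Only the third row differs. The one place that links anaphylaxis to a grade is the DLT list in 3.1.1, which names it with Grade 4 infusion-related events. That line defines a DLT. It does not tell sites how to grade anaphylaxis, and neither Table 6 nor 5.6.1 refers to it.

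**4. How do the neighbouring tables handle a stop at any grade?** Table 5 gives symblepharon an any-grade row, and Table 7 does the same for pulmonary or CNS hemorrhage. Table 6 has no such row, so a reader used to those tables could conclude that no such stop exists for infusion reactions. Section 5.2.3 also lets dosing resume once an event has improved as the 5.3 mitigation plans indicate.

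**The case against.** The strongest reply is that no contradiction exists. Section 5.6.1 is a specific rule for anaphylaxis and can be read as an exception to a general table. The restart is discretionary, so a site can satisfy both passages by not using it. In the only place where the documents attach a grade to anaphylaxis, the two sections agree. This stands as far as it goes. A reader might infer that the Protocol orders two opposite actions for the same reaction; it does not. Nor does 5.3.2 say that Grade 2 or first Grade 3 reactions include anaphylaxis: it says so of infusion reactions as a class. Nor does Table 6 provide for restart within an hour: the hour limits symptom resolution. What remains is that nothing says 5.6.1 prevails, the reference runs one way only, and Table 6 does not exclude a lower-graded anaphylactic reaction.

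A reader might also lean on 7.7.8.2, which says of infusion reactions: "Instead, record each sign or symptom as an individual AE". That governs case report form entries, not treatment decisions, and anaphylaxis is not among the terms it bars. It does not stop an investigator from recognising anaphylaxis and applying 5.6.1.

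On observation, the reply is that cycles was used loosely for infusions. The 2-hour consequence after a reaction is indeed worded by infusion in both sections, which supports that intent. The words after the first infusion in the trigger could also be stretched to cover Day 8, though the mention of later cycles would then be redundant. It would be too strong to say that no observation ever applies to these visits: a patient who reacted to the first infusion gets 2 hours at both. Intent does not close the gap for a patient with no prior reaction, because no other passage states a period.

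**Conclusion.** The point holds as two items to reconcile, both small and both bearing on safety conduct.

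- **Observation.** On the literal text, two of the three Cycle 1 dose-dense infusions have no stated period for a patient without a prior reaction. This rests on reading cycles as the Protocol uses the word elsewhere. It applies to every dose-dense patient as scheduled, and in the run-in both infusions are in the DLT window.
- **Anaphylaxis.** Table 6 lacks an exception or pointer to the unconditional rule in 5.6.1. The two could lead to different handling only if an anaphylactic reaction were graded below 4 and managed from Table 6 alone. The documents neither describe that case nor exclude it.

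Two further inferences are not supported. A reader might expect DLT counts to depend on which section a site followed. They do not: the DLT criteria in 3.1.1 refer to neither Table 6 nor 5.6.1. A reader might also want a number of patients exposed to the anaphylaxis conflict. The documents give no anaphylaxis rate, so none is claimed.

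**What to change.** 1. In Protocol 5.6.1, reword the observation sentence by infusion, so that every dose-dense infusion, including Cycle 1 Days 8 and 15, has a stated period. Reword the trigger sentence in 5.3.2 and 5.6.1 in the same way. The length of the period is for the sponsor's clinicians.
2. Reconcile Table 6 with 5.6.1 by adding an anaphylaxis row or a cross-reference, so that a site using the table finds the rule that governs anaphylaxis. Which rule applies is for the sponsor's clinicians.

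The cost is a few reworded sentences and one table row or reference. No visits are added. Any extra time on site at Cycle 1 Days 8 and 15 depends on the period chosen. The SAP needs no change.
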